b Including participants enrolled in the safety run-in at the confirmed safe dose.

Abbreviations: DLT: dose limiting toxicity; N: number.

Special considerations pertaining to methodology

Interactive Response Technology will be used to control recruitment, assignment per site and facilitate the handling, management, and accountability of drug supply.

Number of participants:

Please refer to the individual substudy for the numbers of participants to be enrolled and treated at the confirmed safe dose.

Note: Enrolled participants are all participants from screened participants who have been allocated to an intervention regardless of whether the intervention was received or not.

Intervention groups and duration:

The duration of the study for a participant will include:

- **Screening period:** Up to 28 days.
- **Treatment Period:** Enrolled participants will receive continuous treatment until PD, unacceptable adverse event (AE), or other full permanent discontinuation criteria as described in [Section 7](#), or complete the maximum cycles allowed in the individual substudy. However, treatment beyond PD may be allowed for up to 9 weeks if the participant appears to be benefiting clinically after discussion with the Sponsor.
- **End of Treatment and Follow-up:** End of Treatment Visit will occur 30 days \pm 7 days from last IMP administration or prior to initiation of further therapy. Participants will then enter the **Observation period** and will be followed differently depending on the reason leading to **End of Treatment (EOT)**:
 1. Participants who discontinue study treatment **without PD** or who **complete the maximum cycles allowed in the individual substudy without PD** (per Lugano response criteria 2014[[2](#)]), will be followed every 3 months \pm 7 days from last IMP administration, for safety (as per Schedule of Activities [SoA] in the individual substudy) and tumor imaging assessments, until PD, start of another anticancer therapy, final cohort cut-off, whichever comes first, before moving to the Survival Phone Call Follow-Up Period.
 2. Participants who discontinue study treatment **with PD** (per Lugano response criteria 2014[[2](#)]) will be followed for safety in the Follow-Up Visit 1 occurring 3 months \pm 7 days from last IMP administration, before moving to the Survival Phone Call Follow-Up Period.

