1.4 BIOMARKER FLOWCHARTS

1.5 PHARMACOKINETIC FLOWCHARTS

Cycle	Treatment Cycle 1					Treatment Cycle 2, 4, 7, 10 + every 5 th cycle		EOT visit	
Day	D1			D2	D3	D8	D1		30 (± 7) days after last IMP administration
Time after start of SAR444245 dosing [h]	SOI	EOI	4h post EOI	At any time	At any time	At any time	SOI	EOI	At any time
SAR444245 PK sample		P00 ^b	P01	P02 ^c	P03 ^c			P00 ^b	
SAR444245 ADA sample	AB00 ^a					AB01	AB00 ^a		ABF00

a Samples collected strictly before start of infusion (SOI). ADA sampling may be discontinued by the Sponsor once sufficient data have been collected.

b PK sample must be taken at the end of infusion (EOI) after flush.

c P02 and P03 to be collected during safety run-in and when participants are hospitalized.

In the event the infusion is interrupted, a PK sample should be drawn immediately after interruption. If infusion is not likely to be resumed by clinical assessment, subsequent samples should be drawn at 4 h after interruption. If infusion is resumed, a (further) PK sample should be drawn at end resumed infusion and subsequent sample should be drawn at 0.5 h after end of resumed infusion. PK sampling may be discontinued by the Sponsor once sufficient data have been collected.

Abbreviations: ADA: anti-drug antibodies; D: day; EOT: end of treatment; PK: pharmacokinetic.

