1.5 PHARMACOKINETIC FLOWCHARTS

Cycle	Treatment Cycle 1					Treatment Cycle 2, 4, 7, 10 + every 5 th cycle		EOT visit	
Day	D1			D2	D3	D8	D1		30 (± 7) days after last IMP administration
Time after start of SAR444245 dosing [h]	SOI	EOI	4h post EOI	At any time	At any time	At any time	SOI	EOI	At any time
SAR444245 PK sample		P00 ^b	P01	P02 ^c	P03 ^c			P00 ^b	
SAR444245 ADA sample	AB00 ^a					AB01	AB00 ^a		ABF00

a Samples collected strictly before start of infusion (SOI). ADA sampling may be discontinued by the Sponsor once sufficient data have been collected.

b PK sample must be taken at the end of infusion (EOI) after flush.

c P02 and P03 to be collected during safety run-in and when participants are hospitalized.

In the event the infusion is interrupted, a PK sample should be drawn immediately after interruption. If infusion is not likely to be resumed by clinical assessment, subsequent samples should be drawn at 4 h after interruption. If infusion is resumed, a (further) PK sample should be drawn at end of resumed infusion and subsequent sample should be drawn at 0.5 h after end of resumed infusion. PK sampling may be discontinued by the Sponsor once sufficient data have been collected.

Abbreviations: ADA: anti-drug antibodies; D: day; EOT: end of treatment; PK: pharmacokinetic.

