3 STATISTICAL ANALYSES

3.1 GENERAL CONSIDERATIONS

In general, continuous data will be summarized using the number of observations available, mean, standard deviation (SD), median, minimum, and maximum. Categorical and ordinal data will be summarized using the count and percentage of participants.

The baseline value is defined as the last available value before the first administration of any of the two IMPs (SAR444245 or pembrolizumab). For participants enrolled but not treated, the baseline value is defined as the last available value before enrollment.

Unless otherwise specified, analyses will be performed by cohort, by dose level (if applicable) and overall. Participants enrolled in the safety run-in part and treated at the RP2D will be included in the analyses of the core part.

All efficacy analyses will be performed on the efficacy population. Complete response rate (CRR, for cohort A) and objective response rate (ORR, for cohort C1), as well as all other response-related efficacy endpoints will be derived using the Investigator's assessment per Lugano response criteria 2014 for all cohorts.

All safety analyses will be performed on the exposed population.

Central imaging may be done retrospectively if significant activity is observed (See [Section 3.2.3](#) for sensitivity analysis).

Confidence intervals will be two-sided 90% CI for efficacy analyses. CI will be used for descriptive purposes only, without inference.

The BOR is defined as the best overall response observed from the date of first IMP until disease progression, death, cut-off date or initiation of subsequent anti-cancer therapy, whichever occurs first.

Analysis period

The analysis period will be divided into 3 segments:

- The **pre-treatment period** is defined as the time from when the participants give informed consent to the first administration of the IMP.
- The **on-treatment period** (i.e., treatment-emergent (TE) period) is defined as the time from the first administration of IMP up to 30 days after the last administration of IMP.
- The **post-treatment period** is defined as the time from the end of the on-treatment, ie. 31 days after the last administration of IMP.

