3.7.1.2 Immunogenicity analyses

Participant's ADA status, response variable and kinetics of ADA responses (see definitions below) will be summarized on the ADA population.

Kinetics of ADA responses will be described for participants with treatment-induced ADA and for participants with treatment-boosted ADA, separately. Time to ADA onset and duration of ADA will be described with minimum, Q1, median, Q3 and maximum statistics.

Peak titer will be described with minimum, Q1, median, Q3 and maximum statistics for participants with treatment-induced ADA and for participants with treatment-boosted ADA, separately.

ADAs against SAR444245 (negative, positive, inconclusive) and corresponding titers, ADAs directed against PEG moiety of SAR444245 status (negative, positive,) and ADAs cross-reacting with endogenous IL-2 status (negative, positive) will also be described overtime using descriptive statistics.

ADAs directed against PEG moiety of SAR444245 status and ADAs cross-reacting with endogenous IL-2 status will only be determined if ADAs against SAR444245 status is positive.

The impact of positive immune response on efficacy, PK and safety variables may be further explored, depending on ADA incidence.

Participant's ADA status against SAR444245

- Participants with **pre-existing ADAs** correspond to participants with ADAs present in samples drawn before first administration of intervention. Participants with missing ADA sample at baseline will be considered as without pre-existing ADA.
- Participants with **treatment-emergent ADA** correspond to participants with at least one treatment-induced/boosted ADA.
 - Participants with **treatment-induced ADAs** correspond to participants with ADAs that developed during the treatment-emergent (TE) period and without pre-existing ADA (including participants without pre-treatment samples).
 - Participants with **treatment-boosted ADAs** correspond to participants with pre-existing ADAs that are boosted during the TE period to a significant higher titer than the baseline. A 2-fold serial dilution schema is used during titration, so at least a 4-fold increase will be considered as significant.
- Participants with **unclassified ADA** correspond to participants with pre-existing ADAs that cannot be classified as treatment-boosted ADA because of missing titer(s) (i.e., a positive ADA sample during the TE period in a participant with pre-existing ADA but with missing titer at this sample or at baseline).

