- Participants **without treatment-emergent ADA** correspond to participants without treatment-induced/boosted ADA and without any inconclusive sample nor unclassified ADA during the TE period.
- Participants **with inconclusive ADA** are defined as participants which cannot irrefutably be classified as with or without treatment-emergent ADA.

Kinetics of ADA response

[figure not shown]
Kinetics of ADA response will be derived for participants with treatment-induced/boosted ADA considering ADA samples collected during the TE period and post-treatment period.

- **Time to onset of ADA response** is defined as the time period between the first IMP administration and the first treatment-induced/boosted ADA.
- **Duration of ADA response** is defined as the time between the first treatment-induced/boosted ADA and the last treatment-induced/boosted ADA, irrespective of negative samples or positive samples not reaching the boosted threshold in-between. ADA duration will be summarized only for participants with persistent ADA response.
 - A positive sample (boosted positive sample for participants with pre-existing ADA) occurring after the TE period will be considered as treatment-induced/boosted ADA if a previous treatment-induced/boosted ADA occurred during the TE period and less than 16 weeks before this sample.
- **Persistent ADA response** is defined by treatment-induced/boosted ADA with a duration of ADA response of at least 16 weeks.
- **Transient ADA response** is defined by treatment-induced/boosted ADA with a duration of ADA response of less than 16 weeks and the last sample of the TE period is not treatment-induced/boosted.
- **Indeterminate ADA response** is defined by treatment-induced/boosted ADA that are neither persistent nor transient.

ADA response variable:

- **ADA incidence** is defined as the proportion of participants found to have seroconverted (treatment-induced ADAs) or boosted their pre-existing ADA response (treatment-boosted ADAs) at any time point during the TE period.
- **Incidence of ADAs** directed against PEG moiety of SAR444245 is defined as the proportion of participants with ADAs directed against PEG moiety of SAR444245 during the TE period among evaluable participants. Participants from ADA population are evaluable for ADAs directed against PEG moiety except if ADAs directed against PEG moiety status is not determined on an ADA against SAR444245 positive sample

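### A first positive ADA result at an on-schedule end-of-treatment sample drawn 31 to 37 days after the last dose falls outside the treatment-emergent period and cannot enter ADA incidence, so incidence can be understated

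*SAP*

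**What the plan says.** **Sampling.** The PK flowcharts (section 1.5 of Substudy 01 and of Substudy 03) schedule ADA samples before the first infusion, on Cycle 1 Day 8, before the infusion at "Treatment Cycle 2, 4, 7, 10 + every 5"th cycle, and at the EOT visit (ABF00), "30 (± 7) days after last IMP administration". The master protocol synopsis allows the EOT visit to come earlier: 30 ± 7 days "from last IMP administration or prior to initiation of further therapy".

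**Analysis period.** SAP 3.1 defines the on-treatment (TE) period as "the time from the first administration of IMP up to 30 days after the last administration of IMP". The post-treatment period starts "31 days after the last administration of IMP". Master protocol 9.4.1 has the same Day 30 limit.

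**Classification.** In SAP 3.7.1.2, treatment-induced ADAs "correspond to participants with ADAs that developed during the treatment-emergent (TE) period and without pre-existing ADA". Treatment-boosted ADAs must likewise be boosted in the TE period. ADA incidence is the proportion who seroconvert or boost within that period. The incidences of ADA against the PEG moiety and of ADA cross-reacting with IL-2 carry the same limit. Under duration of response, a positive after the TE period is accepted as induced or boosted "if a previous treatment-induced/boosted ADA occurred during the TE period and less than 16 weeks before this sample".

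**Denominator.** The ADA population (SAP Table 4) needs one ADA result at any time after the first dose, with no TE restriction. The only data-handling convention that mentions ADA (SAP Appendix 5) concerns unscheduled visits.

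**The concern.** A sample drawn exactly as the protocol permits counts on Day 30 and does not count on Day 31. Nothing about the participant or the assay differs between those days; only the date of the clinic visit does. The effect runs one way, because a late first positive can be dropped from the numerator but never from the denominator.

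Incidence of ADAs against SAR444245 is a named secondary endpoint. ADA sampling is sparse, so for participants who stop treatment between two on-treatment samples ABF00 may be the only scheduled look at antibodies after the early doses. Those are the participants for whom losing it from the incidence figure matters most.

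**Working it through.** The documents give no ADA incidence or precision figure to reproduce, so the check is calendar arithmetic on the stated windows.

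1. **Permitted days for ABF00.** 30 − 7 = 23 and 30 + 7 = 37, so Days 23 to 37 after the last dose, which is 37 − 23 + 1 = 15 days.
2. **Split at the end of the TE period.** Days 23-30 are inside (8 days) and Days 31-37 are outside (7 days). 7/15 = 46.7% of permitted days.
3. **A first positive on Day 33, taken through the rules.**
   - Treatment-induced definition: the finding falls after the TE period, so it is not met.
   - Incidence definition: it requires seroconversion within the TE period, so it is not met.
   - Duration sub-rule: it needs an earlier positive in the TE period. By construction there is none.
   - ADA population: there is a post-dose result, so the participant is in the denominator.
   - Label: *without treatment-emergent ADA*, unless a TE sample was inconclusive or unclassified. In that case the label changes, but the participant is still not counted in incidence.

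   A first boosted titer at that sample goes the same way.
4. **Value of one case.** With 25 ADA-evaluable participants, 1/25 = 4.0 points; for example, 3/25 = 12% becomes 4/25 = 16%. With 20 evaluable, 1/20 = 5.0 points.
5. **Who depends on ABF00.** In study days, D1 of cycle *c* is 1 + (*c* − 1) × cycle length.

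| | Cohort A (21-day cycles) | Cohort C1 (14-day cycles) |
|---|---|---|
| C2D1 | Day 22 | Day 15 |
| C4D1 | Day 64 | Day 43 |
| C7D1 | Day 127 | Day 85 |
| Example of stopping in a gap | after Cycle 2 or 3 | after Cycle 5 or 6 |
| Last scheduled ADA sample before ABF00 | Day 22 | Day 43 |

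   The first scheduled scan is 63 ± 7 days after the first dose, so stopping for progression at that scan can fall in either gap.
6. **Illustrative size (assumed inputs).** Understatement = share of participants first positive at EOT × share of EOT samples drawn on Days 31-37. Assuming 5% to 20% for the first and 25% to 75% for the second gives 0.05 × 0.25 = 1.25 points to 0.20 × 0.75 = 15 points. With visits spread evenly over the window, it is 0.05 × 7/15 = 2.3 to 0.20 × 7/15 = 9.3 points. None of these inputs is in the documents.
7. **Side effect on response type.** A transient response requires the last TE sample not to be induced or boosted. Take a Cohort A participant whose only positive is at C2D1 and who stops after Cycle 3. A negative ABF00 on Day 29 makes the response transient. The same negative on Day 33 leaves C2D1 as the last TE sample, and the response becomes indeterminate.

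**The case against.** - **The positive result is not lost.** SAP 3.7.1.2 also describes ADA status and titers over time, without a TE restriction, so a Day 33 positive can still be reported there. This stands: the gap is in the incidence figure and the participant's classification, not in detection.
- **The wording leaves room.** An antibody found on Day 33 may have *developed* before Day 31, and there is an inconclusive category for participants who cannot be firmly classified. That is a fair reading of the induced definition alone. It does not rescue the incidence definition, which looks for seroconversion within the TE period, and the duration sub-rule shows that later positives were meant to count only after an earlier one.
- **Few may be affected.** The EOT visit may be brought forward before further therapy, which plausibly moves early progressors to before Day 31, and the sponsor may stop ADA sampling. No document gives a rate of early stopping. Master protocol 2.2.1 cites response rates of 65-87% and 46% PFS at one year for anti-PD1 monotherapy in Hodgkin lymphoma, so early stopping in Cohort A need not be common. These points reduce the number affected; they do not remove the mismatch.
- **The stakes are modest.** The endpoint is descriptive, nothing is tested, and no stated decision depends on it. That is true and limits the priority, but the remedy is correspondingly small.

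**Conclusion.** The point holds as a defect in a stated rule. Followed as written, the SAP leaves a first positive or first boosted titer at a compliant ABF00 on Days 31-37 out of ADA incidence while keeping the participant in the denominator. It should be corrected, at moderate priority.

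Its size is 7 of 15 permitted days, and 4 points per case if 25 participants are ADA-evaluable. It bites hardest on those who stop between sparse samples, and only when ABF00 is drawn after Day 30.

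Three stronger readings are tempting and are not supported:

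- A reader might infer that incidence *will* be understated. It will be only if late first positives occur, and the documents give no basis for estimating how many.
- A reader might take 4 points per case as a ceiling. It is not: with fewer than 25 evaluable participants each case weighs more.
- A reader might extend the argument to EOT laboratory values in the worst-grade tables. Master protocol 9.4.1 sets the on-treatment window at Day 30, and treatment-emergent AEs use that same window. Changing it for laboratory data would depart from the protocol and separate laboratory tables from AE tables.

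**What to change.** Add one sentence to SAP 3.7.1.2: for ADA classification and incidence, including ADA directed against the PEG moiety and ADA cross-reacting with IL-2, the EOT sample ABF00 is assigned to the TE period when it is drawn within the protocol window, that is up to 37 days after the last IMP. A first positive or first boosted titer at that sample then counts as treatment-emergent, and none of the 15 permitted days falls outside.

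The cost is that sentence and one derivation flag, with no new samples or visits. ADA would then have a slightly longer window than AEs, which the sentence should say openly, and reported ADA incidence may become slightly less favourable. The Day 30 definition in SAP 3.1 stays as it is for all other analyses.

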- **Incidence of ADAs cross-reacting with endogenous IL-2** is defined as the proportion of participants with ADAs directed against endogenous IL-2 during the TE period among evaluable participants. Participants from ADA population are evaluable for ADAs directed against endogenous IL-2 except if their status is not determined on an ADA against SAR444245 positive sample.

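### The anti-PEG and IL-2-cross-reacting ADA incidences in SAP 3.7.1.2 carry no baseline condition, so they are on-treatment prevalence labelled as incidence

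*SAP*

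**What the plan says.** SAP 3.7.1.2 lists three incidence measures together under the ADA response variable.

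- **Overall ADA incidence**, the first measure, "is defined as the proportion of participants found to have seroconverted (treatment-induced ADAs) or boosted their pre-existing ADA response (treatment-boosted ADAs) at any time point" in the treatment-emergent (TE) period.
- **Anti-PEG incidence** is "defined as the proportion of participants with ADAs directed against PEG moiety of SAR444245 during the TE period among evaluable participants".
- **IL-2-cross-reacting incidence** is the "proportion of participants with ADAs directed against endogenous IL-2 during the TE period among evaluable participants".

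Members of the ADA population are evaluable for anti-PEG "except if ADAs directed against PEG moiety status is not determined on an ADA against SAR444245 positive sample"; the IL-2 measure has a parallel rule. SAP 3.1 defines the TE period by dates alone: first IMP administration to 30 days after the last.

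The same section already has the concepts needed to separate old antibodies from new ones. Pre-existing ADAs "correspond to participants with ADAs present in samples drawn before first administration of intervention". A missing baseline sample is treated as no pre-existing ADA. For boosting, "at least a 4-fold increase will be considered as significant". These categories are set out only for ADA against SAR444245 as a whole. For the two specificities the SAP plans a positive or negative status, described over time; titers are mentioned only for ADA against SAR444245.

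**The concern.** Three adjacent measures share the word incidence, but only the first requires that something changed after dosing. The other two require presence in a time window. A persistent antibody that predates treatment meets that requirement, so the result is a prevalence.

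The trial can enroll such participants. Exclusion criterion E19 in the master protocol (5.2) removes people with known severe hypersensitivity or a contraindication to PEG or pegylated drugs. It does not screen for antibodies. The SAP itself plans for pre-existing ADA.

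What is at stake is how two secondary tables are read. A figure for antibodies that cross-react with the participant's own IL-2 will draw attention as a safety matter. Placed beside an overall incidence built on the induced-or-boosted rule, it will naturally be read on the same basis. Protocol 9.4.3.7 leaves the immunogenicity analyses to the SAP, so no other text corrects the definition.

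**Working it through.** The documents give no ADA rate and no baseline prevalence, so there is no plan figure to reproduce. The check compares the numerators and then counts under stated assumptions.

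**Step 1: follow individual participants through the SAP 3.7.1.2 rules** (titers available, no inconclusive sample).

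| Baseline | TE period | Overall ADA incidence | Anti-PEG incidence as written |
|---|---|---|---|
| ADA negative | anti-PEG positive | counted (induced) | counted |
| anti-PEG positive | anti-PEG positive, SAR444245 ADA titer up at least 4-fold | counted (boosted) | counted |
| anti-PEG positive | anti-PEG positive, titer unchanged | not counted | **counted** |

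The third row is the discrepancy. That participant is classed as without treatment-emergent ADA. The evaluability rule does not remove the participant, because it depends on whether specificity was determined on a positive sample, not on whether the participant was already positive. The IL-2 measure behaves in the same way.

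**Step 2: size.** Inputs:
- n = 25 evaluable, the planned cohort size (Substudies 01 and 03, section 9.2; SAP section 4), assuming nobody is non-evaluable.
- t = participants with treatment-induced or treatment-boosted ADA, all assumed positive for the specificity.
- k = persisting, unboosted carriers (assumed).

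As written: (t + k)/n. Under the induced-or-boosted rule: t/n. Difference: k/n, so one carrier adds 1/25 = 4 points.

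| t | k | As written | Induced-or-boosted rule |
|---|---|---|---|
| 0 | 1 | 1/25 = 4% | 0% |
| 0 | 3 | 3/25 = 12% | 0% |
| 0 | 5 | 5/25 = 20% | 0% |
| 2 | 1 | 3/25 = 12% | 2/25 = 8% |
| 2 | 3 | 5/25 = 20% | 8% |
| 2 | 5 | 7/25 = 28% | 8% |

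The two rules agree only when k = 0. In every row shown, the specificity figure exceeds the overall ADA incidence of which it would be expected to be a part.

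**Step 3: can the planned data separate the cases?** Largely. A pre-infusion ADA sample (AB00) is scheduled at Cycle 1 Day 1 in both substudies (section 1.5). A baseline sample negative for ADA against SAR444245 is negative for both specificities by construction, since these are determined only on positive samples. Two gaps remain: a positive baseline sample may lack a specificity result, and no specificity titers are planned.

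**The case against.** The best defense is that the definitions state their numerator and window openly, so only the label is at fault. Both specificity statuses will also be described over time. If that display includes the pre-dose visit, baseline positives will be visible. No test, dose decision or stopping rule uses these figures. For the use the SAP does name, exploring whether a positive immune response affects efficacy, PK or safety, counting every antibody present on treatment is reasonable.

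Much of this stands, and it limits the importance of the point. It does not repair the measure. A table over time leaves the incidence numerator unchanged, and a count of antibodies of any origin is a prevalence and should be called one.

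Several stronger readings are tempting but are not supported:

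- **That the SAP attributes these antibodies to SAR444245.** It does not say so. A reader might infer it from the label and the neighboring definition.
- **That specificity will be known for every positive sample.** A positive result is a precondition for determining specificity, not a commitment to do so, and the evaluability rules foresee undetermined cases.
- **That the 4-fold rule could identify boosting of each specificity.** The planned titer is for ADA against the whole molecule. It could rise through a different specificity while the anti-PEG antibody stays constant.
- **That 4% to 20% is an expected inflation.** It follows from assuming 1 to 5 carriers and no treatment-emergent cases.

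**Conclusion.** The inconsistency is in the text and does not depend on any assumption: as defined, the two specificity incidences are on-treatment prevalences. The size does depend on assumptions. It is 4 points per persisting unboosted carrier when all 25 in a cohort are evaluable, and somewhat more per carrier if fewer are. The number of carriers is not given for either specificity, and if there are none the effect is zero.

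The reach is narrow. A reader might suppose that the trial's immunogenicity endpoint is compromised. It is not: the secondary endpoint is incidence of ADAs against SAR444245, and the induced-or-boosted rule governs it. The point is worth correcting because the stated rule yields a mislabelled figure on a question with safety interest, and the correction needs no new data.

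**What to change.** In SAP 3.7.1.2:

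1. Define each specificity incidence as evaluable participants positive for that specificity in the TE period and not positive for it at baseline. A baseline sample negative for ADA against SAR444245 counts as negative. A missing baseline sample follows the SAP's existing rule of no pre-existing ADA.
2. Report baseline-positive participants in a separate pre-existing row for each specificity, noting how many had a boosted SAR444245 ADA titer. Do not count them as specificity incidence, because no specificity titers are planned.
3. Treat participants whose baseline sample is ADA-positive with undetermined specificity as not evaluable for that measure.

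If prevalence is what is intended, rename both measures as prevalence during the TE period and add the baseline row.

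The cost is a few sentences and a table row, with no new samples or assays. The reported specificity incidence may be lower, and boosting of a pre-existing specificity is not captured in it. One difference from overall ADA incidence remains: a participant with pre-existing ADA who gains a new specificity without a 4-fold titer rise would count in the specificity incidence only. A footnote should say so.
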